## 1 GENERAL INFORMATION

### 1.1 Introduction

Acne vulgaris is the most common skin disease in patients with skin of color and second most common in Caucasian population. The global prevalence is thought to be as high as 60-80% in individuals 12-25 years of age. However, it is not limited to only teenagers but also to adults, especially adult females. The pathogenesis of acne is multifactorial. Genetics may also play a role. The treatment pathway should be directed to different pathogenic factors including, excessive sebum production, hyper keratinization, *P. acnes*, and inflammation.

Data is limited for skin of color patients in Phase III registration trials. Data is limited because there are a few studies that focus on patients with skin of color. Therefore, a unique study dedicated to patients with skin of color in a real-world setting will be welcome to add further evidence to phase III data.

Winlevi is the first topical anti androgen and sebum inhibitor approved for acne vulgaris. However, we do not have any clinical experience with Winlevi in treatment for acne

Therefore, it is reasonable to study Winlevi to emulate real life practice.

## 1.2 Study Population

Ten (10) subjects with moderate to severe facial acne vulgaris.

## 2 STUDY OBJECTIVES

The objectives of this study are to observe the efficacy and safety of Winlevi in skin of color patients with acne.

Primary objective: Percent of subjects who are clear or almost clear on IGA scale at week 16.

Secondary objectives:

1. Percent of subjects who are clear or almost clear at weeks [REDACTED]
2. Percent of total lesion reduction at week [REDACTED] compared to baseline
3. Percent of inflammatory lesion reduction at week [REDACTED] compared to baseline
4. Percent of non-inflammatory lesion reduction at week [REDACTED] compared to baseline.
5. Tolerability measures such as, erythema, scaling, dryness, oiliness, burning/stinging, and pruritus.

## 3 STUDY DESIGN

This is a single-center, open-label pilot study. All study subjects will receive both Winlevi at baseline. The duration of the study is [REDACTED] weeks and consists of a Screening, Baseline Visit, and Follow-up Visits at Weeks [REDACTED]. The treatment period is [REDACTED] weeks and [REDACTED] weeks of safety follow up totaling to [REDACTED] weeks.

## 4 SELECTION AND WITHDRAWAL OF SUBJECTS

### 4.1 Inclusion Criteria

- i. Outpatient, male or female subjects of any race (Fitzpatrick skin types IV, V, VI), and at least 12 years of age or older. Female subjects of childbearing potential must have a negative urine pregnancy test result at Baseline (test must have a sensitivity of at least 25mIU/ml for human chorionic gonadotropin) and practice a reliable method of contraception throughout the study:

*A female is considered of childbearing potential unless she is:*

- postmenopausal for at least 12 months prior to study drug administration;
- without a uterus and/or both ovaries; or
- has been surgically sterile for at least 6 months prior to study drug administration.

*Reliable methods of contraception are:*

- hormonal methods or intrauterine device in use  $\geq$  90 days prior to study drug administration;
- barrier methods plus spermicide in use at least 14 days prior to study drug administration; or
- vasectomized partner (vasectomy must be performed 3 months prior to first study drug administration or in the alternative a zero sperm count will suffice)

*[Exception: Female subjects of childbearing potential who are not sexually active will not be required to practice a reliable method of contraception. These subjects may be enrolled at the Investigator's discretion if they are counseled to remain sexually inactive during the study and understand the possible risks in getting pregnant during the study.]*

- ii. Facial acne IGA score of 3 or 4.
- iii. Able to understand the requirements of the study and sign Informed Consent/HIPAA Authorization forms. Subjects under the legal age of consent in the state where the study is conducted must also have the written, informed consent of a parent or legal guardian.

#### **4.2 Exclusion Criteria**

- i. Female subjects who are pregnant (positive urine pregnancy test), breast-feeding, or who are of childbearing potential and not practicing a reliable method of birth control.
- ii. Allergy or sensitivity to any component of the test medications (Section 5.2).
- iii. Subjects who have not complied with the proper wash-out periods for prohibited medications (Supplement I).
- iv. Medical condition that, in the opinion of the Investigator, contraindicates the subject's participation in the clinical study.
- v. Skin disease/disorder that might interfere with the diagnosis or evaluation of acne vulgaris
- vi. Evidence of recent alcohol or drug abuse.
- vii. History of poor cooperation, non-compliance with medical treatment, or unreliability.
- viii. Exposure to an investigational drug study within 30 days of the Baseline Visit.

#### **4.3 Withdrawal of Subjects**

It is the right and duty of the Investigator to discontinue the study participation of a subject when the subject's health or well-being is threatened by continuation in the study. Such subjects should be withdrawn from the study.

The following are circumstances that would result in the subject's discontinuation from the study:

- the subject experiences a serious adverse event rendering them unable to continue study participation;
- the subject is unable to physically or mentally tolerate the use of the test medication;
- an exclusion criterion becomes apparent at any time during the study; or
- the subject voluntarily withdraws.

In the event of premature discontinuation from the study, the Investigator should determine the primary reason for discontinuation. A subject who is withdrawn from the study prior to initiation of treatment may be replaced.

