## 5 TREATMENT OF SUBJECTS AND FOLLOW-UP

### 5.1 Study Procedures

## 5.2 Study Treatment

### 5.2.1 Details of Study Treatment

WINLEVI cream 1% is supplied in [REDACTED]  
[REDACTED] 60-gram tube

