#### 6.2.1 Tolerability

The Investigator will grade the current severity of erythema (disease related and/or related to IP use), dryness, peeling, and oiliness as per the following:

Score	Erythema	Dryness	Peeling	Oiliness
0 = Absent	No redness	None	Smooth	Normal
1 = Trace	Faint red or pink coloration, barely perceptible	Barely perceptible dryness by palpation with no accentuation of skin markings, skin desquamation (flakes) or fissure formation	Fine peeling, barely perceptible	Mild and localized
2 = Mild	Light red or pink coloration	Easily perceptible dryness by palpation with accentuation of skin markings but no skin desquamation (flakes) or fissure formation	Slight peeling	Mild and diffuse
3 = Moderate	Medium red coloration	Easily noted dryness with accentuation of skin markings and skin desquamation (small flakes) but no fissure formation	Definitely noticeable peeling	Moderate and diffuse
4 = Severe	Beet red coloration	Easily noted dryness with accentuation of skin markings, skin desquamation (large	Extensive peeling	Prominent and dense

The **Investigator** will **interview the subject** to determine the *current* severity of pruritus and burning/stinging; these symptoms will be graded as per the following:

Score	Description
0 = Absent	Normal, no discomfort
1 = Trace	An awareness, but no discomfort and no intervention required
2 = Mild	Noticeable discomfort causing intermittent awareness
3 = Moderate	Noticeable discomfort causing continuous awareness
4 = Marked	Definite discomfort causing continuous awareness interfering occasionally with normal daily activities
5 = Severe	Definite, continuous discomfort interfering with normal daily activities

---

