## 7 ASSESSMENTS OF SAFETY

### 7.1 Safety Assessments

Throughout the study, subjects will be monitored for signs and symptoms of adverse events. An *adverse event* is any pathological or unintended change in the structure, function or chemistry of the body that occurs during the study, irrespective of causality, including any illness, injury, toxicity, sensitivity, or sudden death. The condition must either not be present pre-study or must worsen in either intensity or frequency during the study.

A *serious adverse event* is any untoward medical occurrence, that, at any dose:

- results in death;
- is life-threatening;
- requires in-patient hospitalization or prolongation of existing hospitalization;
- results in persistent or significant disability/incapacity;
- is a congenital anomaly/birth defect; or
- is an important medical event.

An *unexpected adverse event* is any treatment-related adverse event, which is not identified in nature, severity, or frequency in current literature on the test product.

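### Section 4.3 ends study participation, not just treatment, for subjects who cannot tolerate the cream, and no readable text secures a later contact for a non-serious reaction

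*Combined protocol and SAP*

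**What the plan says.** Section 4.3 introduces its list with "The following are circumstances that would result in the subject's discontinuation from the study". One item is that "the subject is unable to physically or mentally tolerate the use of the test medication". Voluntary withdrawal is a different item on the same list. After a premature discontinuation, the section asks the investigator only to determine the main reason. On replacement it says: "A subject who is withdrawn from the study prior to initiation of treatment may be replaced".

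Section 2 states: "The objectives of this study are to observe the efficacy and safety of Winlevi in skin of color patients with acne". Tolerability is a secondary objective there and a secondary endpoint in Section 6.2. Section 3 provides for observation after treatment, with the lengths blacked out: "The treatment period is [REDACTED] weeks and [REDACTED] weeks of safety follow up totaling to [REDACTED] weeks".

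Four sections govern what is collected on safety:

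- Section 7.1: "Throughout the study, subjects will be monitored for signs and symptoms of adverse events".
- Section 7.2.2 requires every adverse event, serious or not, to be recorded with severity, onset and stop dates, action taken, and whatever else is needed to evaluate it fully.
- Section 7.2.3 requires clinical follow-up to resolution or explanation, for serious adverse events.
- Section 8.2 analyses all enrolled subjects, tabulates incidence and severity, and lists every report.

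In this copy, "5.1 Study Procedures" is a heading with no text beneath it.

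**The concern.** Stopping a drug and leaving a study are different decisions. Section 4.3 treats them as one for intolerance. A subject whose skin reacts badly has good reason to stop the cream, but that is no reason to stop observing the subject, least of all when safety and tolerability are what the study sets out to observe.

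At stake is the course of the reaction after the cream is stopped: whether it resolves, how quickly, and whether anything appears late. The planned safety follow-up would show this, and the subjects who stopped because of a reaction are those for whom it is most informative. The point concerns safety observation only. The count of intolerance events is not in doubt, and the analysis of the week-16 IGA endpoint is not at issue here.

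**Working it through.** The plan states no figure to reproduce: Section 8.1 sets 10 subjects and gives no formal justification. The check is mainly a reading of sections side by side.

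**1. What ends?** The lead-in to the Section 4.3 list names the study, not the medication. The section's opening paragraph likewise speaks of ending study participation.

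**2. Does it reach willing subjects?** Yes. A subject who wishes to go is covered by the voluntary-withdrawal item. The intolerance item therefore also applies to subjects who would have stayed.

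**3. What is lost by leaving?** Section 3 places the safety follow-up after the treatment period. A subject discontinued from the study during treatment does not reach it.

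**4. Does other readable text restore it?**

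| Section | What it secures for a non-serious reaction | What it leaves open |
|---|---|---|
| 4.3 | Main reason for discontinuation | Any later visit |
| 6.2.1 | Severity grades at a contact | The contact itself: the scales record present severity ("The Investigator will grade the current severity of erythema") |
| 7.1 | Monitoring while in the study | The time after leaving |
| 7.2.2 | Event, severity, onset and stop dates, pertinent data | How a stop date is obtained if the reaction is ongoing at exit |
| 7.2.3 | No stated requirement (serious events only) | Follow-up to resolution |
| 8.2 | Tabulation and full listing, all enrolled subjects | Observations that were never made |

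No readable section names a contact after withdrawal for a non-serious reaction. Section 5.1 might; it cannot be read in this copy.

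**5. Scale.** Each affected subject is 1 of 10, or 10% of the sample. Replacement is provided for only before treatment starts, so a subject who stops for intolerance remains one of the ten.

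The documents give no rate of intolerance, so what follows is an assumption shown as a range. Let p be the chance that a subject stops for non-serious intolerance, and q the share of such subjects with no contact after leaving, with subjects independent.

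- Chance of at least one such stop: 1 − (1 − p)^10
- Chance that at least one later course goes unobserved: 1 − (1 − pq)^10

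| | p = 5% | p = 10% | p = 20% |
|---|---|---|---|
| At least one stop | 1 − 0.95^10 = 40% | 1 − 0.90^10 = 65% | 1 − 0.80^10 = 89% |
| Unobserved, q = 0 | 0% | 0% | 0% |
| Unobserved, q = 0.5 | 1 − 0.975^10 = 22% | 1 − 0.95^10 = 40% | 1 − 0.90^10 = 65% |
| Unobserved, q = 1 | 40% | 65% | 89% |

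The row q = 0 is the case in which Section 5.1, or site practice, already provides a contact for all. The range from 0% to 89% shows that these figures cannot measure the problem in this trial. They show only that in a study of 10 a single stop is plausible under modest assumed rates.

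**The case against.** The strongest reply is that the gap may not exist. Section 5 covers treatment and follow-up, and its first subsection, where an exit visit would normally be described, has no text in this copy. The visit weeks and the length of the follow-up are blacked out. This stands as a limit: it cannot be said that the plan lacks a post-withdrawal contact, only that no readable text secures one. It does not change the wording of Section 4.3, which would still need to agree with any such visit.

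Second, Section 7.2.2 covers all adverse events, is not limited to subjects still enrolled, and asks for a stop date. Section 7.2.3 does not say that non-serious events are dropped. This also stands in large part. What remains is narrow: the stop date is required, but no contact is named at which to learn it, and a late event in a subject who has left has no planned occasion to be reported.

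Third, a reader might infer that a persisting reaction would vanish from the safety results, or that the subject would drop out of the denominator. The documents do not support that. Section 8.2 keeps all enrolled subjects and lists every report, so an event without a stop date would still appear in the listing. Nor does the plan define a proportion with a reaction at the safety follow-up that could be distorted.

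Fourth, keeping these subjects enrolled is not free of difficulty. Supplement I prohibits certain medications during the study (the list is blacked out). A subject with moderate to severe acne who has stopped the cream would either stay under those prohibitions or start another therapy that affects the skin grades. This is a fair objection, and the change has to deal with it.

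Finally, this is a single-center, open-label pilot of 10 subjects with a marketed cream. That bears on how much weight the point carries, but the change is small in proportion.

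**Conclusion.** The point holds in a limited form. As worded, Section 4.3 makes intolerance a reason to leave the study, applies this to subjects willing to stay, and so ends their participation before the safety follow-up in Section 3. The event, its severity and the reason for stopping are kept. What is not secured in readable text is a contact after withdrawal at which the later course of a non-serious reaction, or a late event, could be observed. Subjects whose intolerance is a serious adverse event are followed under Section 7.2.3 and are not affected.

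The size is 1 of 10 for each affected subject; how many there would be is unknown. The conclusion rests on the wording of Section 4.3 being followed literally and on Section 5.1 not already providing a contact. If it does provide one, only an inconsistency of wording remains. This is an inexpensive improvement to safety observation, held with medium confidence. It does not undermine the study's event counts.

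**What to change.** - **Section 4.3:** separate stopping study medication from leaving the study, and keep the reasons for stopping the cream as they are. Unless consent is withdrawn, a subject who stops for intolerance has the Section 6.2.1 grades and an adverse-event review at the time of stopping, and then completes the safety follow-up already planned in Section 3.
- **Supplement I:** state that the prohibitions no longer apply once the cream is stopped, that any new acne therapy is recorded, and that skin grades taken after it begins are reported separately.
- **Section 7.2.3:** extend follow-up to non-serious treatment-related skin events that led to stopping, until resolution or the end of the safety follow-up.
- **If Section 5.1 already provides these contacts:** align Section 4.3 with it.

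The cost is a few sentences and one or two visits for a few subjects, using scales and a follow-up period the plan already has. Some of these subjects will decline to return, and later skin grades may reflect another therapy rather than recovery from the cream.

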### 5.2.7 Treatment Compliance

Subject compliance to study treatment regimen will be assessed at each visit; study personnel will ask each subject whether they missed any applications of study medication since the previous visit.

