## 6 STUDY ASSESSMENTS

### 6.1 Primary Endpoint

The primary endpoint of this study is the percent of patients who achieve clear or almost clear on IGA at week 16.

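### Section 4.3 ends study participation, not only treatment, when any exclusion criterion comes to light, so a treated subject with a late-found entry breach can be lost to the week-16 primary endpoint

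*Combined protocol and SAP*

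**What the plan says.** Section 4.3 introduces its list with "The following are circumstances that would result in the subject's discontinuation from the study". The third of the four items is "an exclusion criterion becomes apparent at any time during the study; or". The list states no investigator discretion, does not separate treated from untreated subjects, and does not distinguish stopping the cream from leaving the study.

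Section 4.2 has eight exclusion criteria. Some concern current status, such as pregnancy. Others describe the subject's past at entry. Criterion vii is "History of poor cooperation, non-compliance with medical treatment, or unreliability". Criterion viii is "Exposure to an investigational drug study within 30 days of the Baseline Visit". Criterion iii concerns wash-out compliance, and its details are in Supplement I, which is redacted.

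On replacement, section 4.3 says only: "A subject who is withdrawn from the study prior to initiation of treatment may be replaced". Under section 5.2.7, "study personnel will ask each subject whether they missed any applications of study medication since the previous visit"; that section sets no threshold and attaches no consequence.

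Section 6.1 states: "The primary endpoint of this study is the percent of patients who achieve clear or almost clear on IGA at week 16". Section 8.1 sets the sample at 10 without formal justification. Section 8.2 calls the analysis intent-to-treat and defines this as including everyone enrolled. It gives no rule for a missing week-16 IGA.

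**The concern.** An exclusion criterion protects entry to the trial. Once a subject has been treated, discovering that an entry-history criterion was breached is an eligibility deviation. An intent-to-treat analysis would normally keep that subject and want the outcome. Section 4.3 instead ends study participation, so the week-16 IGA may never be taken. The subject stays in the denominator under section 8.2 but has no outcome, and the protocol does not say what value to use.

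A second, weaker issue is the reach of criterion vii. It has no look-back date, unlike viii, which is tied to Baseline. Section 4.3 keeps the criteria live throughout the study, and section 5.2.7 has staff ask about missed applications at each visit. Nothing rules out a site treating repeated missed applications as criterion vii. If that happened, the losses would fall on the less adherent subjects. That would fit poorly with the rationale in section 1.1: "Therefore, it is reasonable to study Winlevi to emulate real life practice".

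**Working it through.** **Reading the sections together**

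1. Trigger: any section 4.2 criterion, at any time (section 4.3, third item).
2. Consequence: discontinuation from the study. Section 4.3 contains no provision for continued outcome assessment.
3. Replacement: available only before treatment starts, so a treated subject who is lost is not covered.
4. Analysis: everyone enrolled is included (section 8.2), with no rule for a missing outcome.

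Criterion viii is fixed relative to Baseline, so it cannot newly arise on study; it can only be discovered late. The same reading is the natural one for iii, and for vii because of its opening words. No strained interpretation is needed for a treated subject to be caught by steps 1 to 4.

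**Size**

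Inputs from the protocol: N = 10 (section 8.1) and a binary primary endpoint at week 16 (section 6.1). Section 8.1 gives no response rate, removal rate or dropout allowance, so there is no planned figure to reproduce. Assumed inputs: r = 4 responders among those who stay, and k = 1, 2 or 3 treated subjects removed before week 16.

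Formulas:
- removed counted as non-responders: r / N
- completers only: r / (N − k)
- removed counted as responders: (r + k) / N

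| k | Non-responders | Completers only | Responders |
|---|---|---|---|
| 1 | 4/10 = 40% | 4/9 = 44.4% | 5/10 = 50% |
| 2 | 4/10 = 40% | 4/8 = 50% | 6/10 = 60% |
| 3 | 4/10 = 40% | 4/7 = 57.1% | 7/10 = 70% |

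The distance between the first and last columns is k / N, which is 10 percentage points per removed subject whatever r is.

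For scale, the exact (Clopper-Pearson) 95% interval is 12.2% to 73.8% for 4/10 and 15.7% to 84.3% for 4/8. Sampling uncertainty is therefore larger than the shift. The shift, however, comes from a rule that can be changed before the data are collected.

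**The case against.** **Intent-to-treat already keeps these subjects.** Partly right. Read literally, section 8.2 excludes the completers-only column, because withdrawn subjects stay in the denominator. It does not say whether they count as 40% or 60% in the two-subject example. The lack of a missing-outcome rule is a wider gap that affects every dropout, and changing section 4.3 would not close it. Changing section 4.3 would prevent some of the missing outcomes.

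**The size says nothing specific about this clause.** True. Ten points per subject is simply 1/10 and applies equally to voluntary withdrawal. The documents give no basis for how often the third item would be used.

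**A reader might infer that poor adherers are removed before week 16.** The documents do not support this. Criterion vii opens with a reference to history, which points to behaviour before entry. Section 5.2.7 attaches no withdrawal to missed applications, and section 4.3 does not name non-adherence. Only the ambiguity stands.

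**A reader might also infer that the open-label investigator could use the item to drop subjects who do badly.** Nothing in the documents suggests that use, and other judgement-based exits would remain in any case.

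**A late-found breach might still matter clinically.** This stands. Nothing in the documents shows that such a breach has ceased to affect risk, and Supplement I is redacted. The point therefore concerns outcome collection only.

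**An early-termination assessment may exist elsewhere.** Section 5.1 shows only its heading in the available text, so this cannot be excluded. If one exists, it would need to reach week 16 to answer the point.

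**Conclusion.** The point holds as a wording defect with a modest, avoidable cost. As written, section 4.3 takes a treated subject out of the study when an entry-history breach is found late. No visible provision secures the week-16 IGA, and the replacement rule does not apply, although section 8.2 promises to include that subject. Each case leaves 10 percentage points of the primary result unobserved. With 2 removed and 4 responders among the rest, the result is 40%, 50% or 60% according to handling. Those counts are assumptions; only N = 10 comes from the protocol, and the frequency of such cases is unknown.

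The wording also leaves open whether missed applications on study could count as criterion vii, but it does not say that they do. The real-life aim is background rationale in section 1.1. Because criterion vii already screens at entry, clarifying it would not by itself make the sample representative of ordinary use.

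**What to change.** Reconcile section 4.3 with sections 4.2 and 8.2:

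- When an entry-history criterion (for example vii or viii) is found to have been breached after treatment has begun, record a protocol deviation. Still collect the week-16 IGA, lesion counts and tolerability where the subject agrees, whatever is decided about treatment.
- In section 4.2, state that criterion vii refers to history before Baseline. In section 5.2.7, state that missed applications on study are compliance data.
- Leave the decision on continuing treatment, including after a wash-out breach under criterion iii, as a clinical matter for the sponsor to reconcile in the text. No rule is proposed here.

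The other three items in the section 4.3 list need no change for this purpose.

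The cost is a short amendment with no visits beyond those already planned. The small downside is that subjects with eligibility deviations stay in the data and must be listed in the report.
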